## 7.0 STUDY DESIGN

## 7.1 Summary of Study Design

A prospective, cohort study based at a single centre (Queen Alexandra Hospital, Portsmouth). There is no randomization involved in this study. There is no blinding in this study. There will be a single operator for performing the scans due to the level of

Version 1.0 IRAS 247448

professional training and accreditation required to perform a GLS scan. Expected patient participation is 365 days (+/-7) or until mortality whichever occurs first.

## 7.2 Outcome Measures

Primary outcome measure:

To investigate if 3D left ventricle ejection fraction, or Global Longitudinal Strain, provides an earlier indicator of left ventricle failure in sepsis or septic shock compared to 2D LVEF.

Secondary outcomes measure:

1. To explore any practical barriers to using GLS and three-dimensional echo methods by cardiac physiologists

2. Is three dimensional EF feasible in the ICU population?

3. To investigate whether there is an association between major adverse cardiac events at12 months post sepsis or septic shock and any abnormal echocardiography results at anytime point

4. To investigate whether there is an association between major adverse cardiac events at
12 months post sepsis or septic shock and any abnormal biomarker results at any time point
5. To compare 2D and 3D echocardiographic measurements with GLS to determine whether
currently used definition of abnormality in GLS is appropriate.

6. To compare 2D and 3D echocardiography measurements with GLS to identify if a range of abnormal GLS could be mapped to ranges of abnormal echocardiography results

7. To compare troponin and BNP results with GLS to identify if a range of abnormal GLS could be mapped to ranges of abnormal biomarker results

8. Can troponin or pro NT BNP measurements in combination with 3d LVEF, 2d LVEF or GLS provide an earlier indicator of LV failure in sepsis or septic shock

Safety outcomes:

- Any adverse events during performing the study procedures (AE's)
- Any adverse device events (ADE's)

### **8.0 STUDY PARTICIPANTS**

#### 8.1 Study Setting

Participants will have been admitted to Queen Alexandra Hospital, critical care unit with sepsis or septic shock as defined by The Third International Consensus Definitions for Sepsis and Septic Shock (Sepsis-3) [20].

### 8.2 **Overall Description of Study Participants**

Sepsis or septic shock patients within the first 24 hours of their admission to critical care. Eligibility will be met by the following inclusion and exclusion criteria:

## 8.3 Eligibility Criteria

Inclusion Criteria

- 1. Age 18-85yrs inclusive
- 2. Sepsis or septic shock as defined by Third International Consensus Definition for Sepsis and Septic Shock (Sepsis-3)
- 3. Admission to ICU
- 4. Informed consent taken after discussion with participant or with consultee if appropriate and a period of reflection of up to 18hours. All participants or consultees will have PIS given. Please refer to section 10.1 and 10.2 discussing the issues concerning consent in an unconscious participant

#### **Exclusion Criteria**

The exclusion criteria below specify conditions where the assessment of cardiac function is known to be altered or may not be reliable by the scanning method employed.

- 1. Pregnancy or complications thereof
- 2. ESRF requiring dialysis or CKD with eGFR<30ml/min
- 3. Cardiac transplant recipient
- 4. Uncorrected valvular dysfunction (graded as moderate or severe)
- 5. Known structural heart disease
- 6. Pre-existing cardiomyopathy with bundle block on ECG
- 7. Previous cardiac valve replacement

- 11. Post-operative within last 7 days
- 12. Atrial fibrillation/flutter or frequent ventricular ectopic beats during image acquisition
- 13. Death likely within 24 hours in the opinion of the assessing clinician

#### 9.0 SAMPLING

The minimum sample size is 108. This was based on the use of repeated measures ANOVA comparing three arms at 4 time points, with the significance level of 5% and power of 90%. This is based on a medium assumed effect size 0.15.

Considering that echo image quality is unknown until after consent and enrolment onto study and 20% inflation to study size was added from the original calculated 89, meaning a total of 108 participants

## **10.0 STUDY PROCEDURES**

Items in bold denote additions to standard care

	First 24 hours	At 72 hours	30 days	90 days		
General procedures and safety						
Informed consent	Х					
Demographics	Х					
Medical and surgical history	Х					
Vital signs (BP, HR)	Х	Х	Х	Х		
Weight	Х		Х	Х		
PEEP	Х	Х	Х	Х		
Adverse events potential	Х	Х	Х	Х		
Concomitant therapy	Х	Х	Х	Х		
ECG	Х			Х		
2D ECHO	Х	Х	Х	Х		
Local laboratory						
Chemistry	Х	Х	Х	Х		
Haematology	Х	Х	Х	Х		
Urinalysis	Х			Х		
Hs Troponin	Х		Х	Х		
BNP/NT-proBNP	Х		Х	Х		

Investigational tool						
3D ECHO	Х	Х	Х	Х		
GLS	х	Х	Х	Х		
СО	Х	Х				
MACE follow up call/notes review at 12 months						

Table 2). Schedules of all procedures

#### 10.1 Recruitment

The study will be conducted at Queen Alexandra Hospital, Portsmouth, under the lead of [name], with recruitment assistance from ICU research nurses and ICU team. Research staff alongside the clinical team will be involved in the identification of patients, which will take place on the critical care unit within 24 hours of admission and meeting sepsis 3 criteria for septic shock. If appropriate the participant will be given PIS regarding the study. If the participant is not able to receive the PIS due to lack of capacity then their representative will be given the information. Opportunity will be given to ask questions.

## 10.2 Screening and Enrolment

Patients already enrolled in other research trials will be invited and allowed to participate in the study if they so wish. This was discussed with public and patient involvement (PPI) representatives who felt that these patients should also have the opportunity to participate in the study, and should not be excluded.

If appropriate the participant will be given participant information sheet (PIS) regarding the study. If the participant is not able to receive the PIS due to lack of capacity then their personal consultee will be given the information.

Opportunity will be given to ask questions. Informed consent will be obtained prior to study procedures being undertaken. If informed consent cannot be obtained immediately we refer to the guidance provided by the MRC, on medical research involving adults who cannot consent (2007).

In the majority of cases it will not be possible to obtain consent from the participant at the time of enrolment. If informed consent cannot be obtained immediately we refer to the guidance provided by the MRC, on medical research involving adults who cannot consent (2007)

Participants having reduced level of consciousness due to illness or sedative medication used as part of their treatment. This makes attempts to obtain prior informed consent from the patient challenging and the following measures have been put in place:

#### Patient consent

Participants will need full capacity to consent. If they are unable to gain capacity to consent within 18hrs of meeting study eligibility, we will use personal consultee consent as outlined below. For participants able to consent, a written Participant Information Sheet (PIS) will be provided to the patient. A Consent Form will be provided indicating that:

- The information given, orally and in writing, has been read and understood
- Participation is voluntary and can be withdrawn at any time without consequence;
- That consent is given for access to medical records for data collection.

The Consent Form will also cover ongoing data collection and follow-up.

Participants will be given time to read the PIS and have an opportunity to ask any questions they may have about participation. After verifying that the PIS and Consent Form are understood, the person seeking consent will invite the patient to sign the Consent Form and will then add their own name and countersign it. A copy will be given to the patient, a copy placed in the patient's medical notes and the original kept in the Investigator Site File. If the participant is unable to physically sign the Consent Form (e.g. due to weakness, reduced dexterity), an independent witness can sign on their behalf.

The patient's General Practitioner will then be sent a letter by the recruiting site to inform them of their patient's participation in the study (provided consent has been given for this).

## Personal Consultee

Due to the severity of illness and its impact on the mental state of the target population, it may not be possible to involve participants in the consenting process early on. Instead, consent will be obtained from patients once they have stabilised and are deemed to have capacity.

In the interim, once notified of the potential enrolment of a patient, a delegated member of the site research team will approach relative, friend or legal representative (Personal Consultee) as soon as appropriate and practically possible to discuss the study and to seek their opinion as to the patients' likely wishes and feelings regarding participation.

A separate consent form will be provided indicating that: the information given, orally and in writing, has been read and understood; the patients' participation is voluntary and can be withdrawn at any time without consequence; and that, in the Personal Consultees opinion, the patient would not object to taking part in research. Personal Consultees will also be

asked to indicate whether, in their opinion, the patient would agree to access to medical records for data collection.

### **10.3 Study Assessments**

The overview of the study and schedule of assessments are outlined in Figure 1 and Table1 respectively. Once potential participants are identified and enrolled, the following assessments will take place:

- At baseline and within the first 24 hours, consent where able followed by collection of demographic and basic physiological data (standard to the monitoring of the critically unwell patient).
  - Ventilator settings (Positive End Expiratory Pressure, Pressure Support, inspired oxygen)
  - Estimated or actual weight as documented in patient notes
  - Urinalysis
  - ECG
  - Mean arterial pressure (MAP) and vital signs

Documentation will record medical drug history and currently given. In addition to baseline laboratory tests, biomarkers (high sensitivity troponin and NT-proBNP) will be requested. Within the first, 24 hours the echo scan will be performed.

- At 48-72 hours after the first scan, excluding baseline demographic information a repeat assessment will be performed. This will not include biomarker samples on this occasion.
- At 30 days, excluding baseline demographic information, a repeat assessment will be performed including biomarker samples.
- At 90 days, excluding baseline demographic information, a repeat assessment will be performed including biomarker samples.
- 12 months (+/- 5 days) post inclusion MACE evaluation by notes review and/or telephone call conversation

Demographics, medical and surgical history is available from the patient medical records.

The critical care unit in QAH operates an electronic patient information system, which facilitates with ease other secondary outcomes measure (vital signs, weight, PEEP, concomitant therapy, laboratory results) at the specified time points. Once the patient has

been discharged from critical care this information is no longer available in electronic format and will have to be retrieved manually.

A 12 lead-ECG will be recorded with the use of the hospital's standard machine by staff who are trained on its use.

Laboratory assessments during admission for illness will include basic biochemistry and haematology. Biomarker assessments will have to be requested with prior agreement with the research laboratory based at QAH. The total volume of blood to be drawn for biomarker assessments will not exceed 10mls and will be divided into an EDTA (ethylenediaminetetraacetic acid) and SST (serum separating tube) bottle. The total volume to be drawn over the study for biomarkers and basic laboratory studies will not exceed 90mls.

Once participants have been discharged from critical care, they will be offered follow-up appointments at 30 days and 90 days from point of admission. If they remain within the hospital at 30 and 90 days, then assessment can be done whilst they are an inpatient.

MACE evaluation recorded at 12 months via notes review and/or telephone call to participant by heart failure nurses specialist to identify any out of area hospital admissions/interactions that are recorded as major adverse cardiovascular events such as: MI, stroke, hospitalization because of HF; and revascularization, including percutaneous coronary intervention, and coronary artery bypass graft

Some participants may be lost to follow-up or withdrawn from the study. This is detailed in section 10.5.

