Study Design	A single site, prospective, cohort study.			
Study Participants	
 
In-patients at Queen Alexandra Hospital, Portsmouth with Sepsis and septic shock, specifically:
 
1. Age 18 - 85yrs inclusive
 
2. Sepsis and septic shock as defined by Sepsis-3 criteria
 
3. Admitted to the Intensive Care Unit (ICU)
 
			
Planned Sample Size	108			
Follow-up duration	1yr			
Planned Study Period	3 years			
Primary Objective	• Can 3D LVEF, or GLS, provide an earlier indicator of LV failure in sepsis and septic shock compared to 2D LVEF?			
Secondary Objectives	
 
To explore any practical barriers to using GLS and three- dimensional echo methods by cardiac physiologists
 
Is three-dimensional EF feasible in the ICU population?
 
To investigate whether there is an association between major adverse cardiac events at 12 months post sepsis or septic shock and any abnormal echocardiography results at any time point
 
			

	
 
To investigate whether there is an association between major adverse cardiac events at 12 months post sepsis or septic shock and any abnormal biomarker results at any time point
 
To compare 2D and 3D echocardiographic measurements with GLS to determine whether currently used definition of abnormality in GLS is appropriate.
 
To compare 2D and 3D echocardiography measurements with GLS to identify if a range of abnormal GLS could be mapped to ranges of abnormal echocardiography results
 
To compare troponin and BNP results with GLS to identify if a range of abnormal
 

	biomarker results
Endpoints	• GLS at 24h, 72h, 30 days and 90 days
	• 2D EF and 3D EF at 24h, 72h, 30 days and 90 days
	• NT-proBNP at 24h, 72h, 30 days and 90 days
	High sensitivity troponin at 24h, 72h, 30 days and 90 days
	ICU mortality
	In hospital mortality
	• 30 or 90 day mortality
	
 
hospital re-admission of any cause
 

	Major adverse cardiovascular events (MACE) at 12 months
Eligibility Criteria	Inclusion criteria:
	1. Age 18-85yrs inclusive
	2. Sepsis or septic shock as defined by Third International Consensus Definition for Sepsis and Septic Shock (Sepsis-3)
	3. Admission to ICU
	
 
Informed consent taken after discussion with participant or with consultee if appropriate and a period of reflection of up to 18hours. All participants or consultees will be given Patient information sheet (PIS). Please refer to section 10.1 and 10.2
 

lin.

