#### Diagram 2). Overview of study pathway

## 10.4 Discontinuation/Withdrawal of Participants from Study Treatment

Participants have the right to withdraw from the study at any time and for any reason without prejudice to their future medical care. Likewise the consultees have the same right to withdraw consent at any point while they are acting in that capacity. The investigator should document withdrawal for any reason in the source documents and in the case report form (CRF). Data taken up to point of withdrawal will be utilised, but this will be made clear during the consent process and on any PIS given to the participant. Reasons for removal or reduced follow-up from the study:

- Participant not able to attend follow-up visits, but may still be contacted by telephone or email for 12 months time point enquiry into adverse events/MACE
- By assessment of the investigator or clinician not to continue due to safety concern (e.g. adverse event, pregnancy)
- Palliation for end of life care

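### Any-cause hospital re-admission is a synopsis endpoint, but the only step that looks for admissions at other hospitals is limited to MACE, so non-MACE re-admissions elsewhere are not sought

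*Protocol*

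**What the plan says.** The endpoint list in the Protocol synopsis (section 2.0) contains "hospital re-admission of any cause" and, as a separate item, "Major adverse cardiovascular events (MACE) at 12 months". The MACE item carries a time point; the re-admission item carries none.

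Section 10.3 describes one contact after day 90: "12 months (+/- 5 days) post inclusion MACE evaluation by notes review and/or telephone call conversation". The same section gives the purpose of that contact as "to identify any out of area hospital admissions/interactions that are recorded as major adverse cardiovascular events", and names MI, stroke, hospitalisation for heart failure and revascularisation as examples. Table 2 in section 10.0 enters the step as "MACE follow up call/notes review at 12 months".

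Section 10.4 adds that participants who cannot attend visits "may still be contacted by telephone or email for 12 months time point enquiry into adverse events/MACE".

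Re-admission is not named in the objectives (section 6), the outcome measures (section 7.2), the assessments (section 10.3), either schedule of procedures (Table 2 and Appendix 1) or the analysis section (14).

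**The concern.** The endpoint covers every cause of re-admission, but the procedure that reaches beyond the study hospital asks only about a defined set of cardiovascular events. This is a single-centre study, and section 10.3 uses the 12-month contact to find out-of-area events. The protocol thus recognises that local records alone may not show them.

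At stake is the meaning of the re-admission figure. A sepsis survivor admitted to another hospital with a new infection is not asked about it. The same admission at the study hospital could be found in the local notes, and a heart failure admission at the other hospital falls within the 12-month enquiry. Whether an event is found then depends on its cause and place, which an any-cause endpoint should not do. A SAP can define how re-admission is analysed, but it cannot recover events that nobody asked about.

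**Working it through.** The protocol states no figure for this endpoint, so there is none to reproduce. The check compares the endpoint with each route by which a re-admission might be captured.

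| Route | Where described | Captures a non-MACE re-admission at another hospital? |
|---|---|---|
| 12-month notes review and/or call | 10.3, Table 2 | No; the enquiry is limited to MACE |
| 30- and 90-day visits | 10.3 | Not stated; they repeat the clinical assessment and samples, and re-admission is not named |
| 12-month enquiry for participants who cannot attend visits | 10.4 | No; it covers adverse events and MACE. Section 7.2 confines adverse events to those arising during study procedures, and section 12.0 rules out formal recording of them |
| Notes, clinic letters and clinical databases transcribed to the CRF | 13.1 | Not reliably; a general route that may show local admissions, with nothing to ensure that those elsewhere appear |

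No described route seeks the event in question.

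**Illustration of size.** All inputs are assumptions. Let *o* be the share of re-admissions that are out of area and *m* the share of those that are not MACE. Suppose, favourably, that every local re-admission and every out-of-area MACE is found. Then:

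missed share = *o* × *m*

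observed rate = true rate × (1 − *o* × *m*)

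- *o* = 0.10, *m* = 0.70: missed 0.10 × 0.70 = 0.07, or 7%.
- *o* = 0.20, *m* = 0.90: missed 0.20 × 0.90 = 0.18, or 18%.
- *o* = 0.30, *m* = 0.90: missed 0.30 × 0.90 = 0.27, or 27%.

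With one re-admission per re-admitted patient:

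| Assumed true rate | Observed, 7% missed | Observed, 27% missed |
|---|---|---|
| 30% | 0.30 × 0.93 = 27.9% | 0.30 × 0.73 = 21.9% |
| 40% | 0.40 × 0.93 = 37.2% | 0.40 × 0.73 = 29.2% |
| 50% | 0.50 × 0.93 = 46.5% | 0.50 × 0.73 = 36.5% |

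The mismatch between endpoint and procedure is in the text and does not depend on these values.

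**The case against.** The best defence is that this is a lightly specified secondary item whose collection is simply not spelled out. Re-admission appears once, as a synopsis bullet, and no stated objective or analysis depends on it. The absence of a schedule row proves little: the ICU, in-hospital and 30- or 90-day mortality endpoints have no row either. Section 13.1 provides a general route from notes and letters to the CRF, and the CRF is not available. With no window stated, re-admission might be meant over 30 or 90 days, in which case the 12-month contact would not be the relevant step.

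Most of this stands, and it sets the severity. It does not remove the gap. The 13.1 route gives no assurance of seeing admissions elsewhere, the 30- and 90-day visits do not mention re-admission, and the one step aimed at other hospitals is confined to MACE. The missing window is itself something to repair.

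A reader might infer three stronger things that the protocol does not support:

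- **That patients with a non-MACE admission elsewhere are counted as not re-admitted.** No coding rule is given; such patients could equally be treated as missing.
- **That the endpoint is firmly tilted towards cardiac causes because MACE are sought everywhere.** The 12-month step is notes review and/or a call, so a notes-only review could miss MACE elsewhere too. The dividing line is also MACE, not cardiac: stroke is included, while a cardiac admission outside the named events, such as arrhythmia, may not be.
- **That a link between abnormal echo results and re-admission would partly repeat the MACE analysis.** The protocol relates echo and biomarker results to MACE at 12 months and plans no such analysis for re-admission.

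**Conclusion.** The point holds as a minor one. Followed as written, the protocol does not seek non-MACE re-admissions outside the study hospital. Its any-cause endpoint would be under-ascertained to a degree that varies with cause and place of treatment. The endpoint also lacks a time window.

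The size cannot be determined from the protocol. The 7-27% range rests wholly on assumed shares and is given only for scale. The conclusion assumes that the CRF, which is not shown, does not ask more than section 10.3 describes. The primary comparison of 2D LVEF, 3D LVEF and GLS and the section 7.2 outcomes are unaffected.

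**What to change.** Amend section 10.3 and Table 2 so that the 12-month notes review/call, and the 30- and 90-day visits, record every hospital admission after index discharge, at any hospital, with date, hospital and main cause. Classify each admission as MACE or not afterwards, so that one record serves both endpoints. State the time window for re-admission in the synopsis.

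If the sponsor does not want to collect this, restrict the endpoint to re-admission to the study hospital and say so. That is simpler, but it answers a narrower question.

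The cost is a slightly longer call and one CRF line, within contacts already planned. The gain is limited where only notes are reviewed, since admissions elsewhere may still not appear in them. The change should be made before follow-up contacts take place, because events not asked about may be hard to recover later.

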#### Diagram 2). Overview of study pathway

## 10.4 Discontinuation/Withdrawal of Participants from Study Treatment

Participants have the right to withdraw from the study at any time and for any reason without prejudice to their future medical care. Likewise the consultees have the same right to withdraw consent at any point while they are acting in that capacity. The investigator should document withdrawal for any reason in the source documents and in the case report form (CRF). Data taken up to point of withdrawal will be utilised, but this will be made clear during the consent process and on any PIS given to the participant. Reasons for removal or reduced follow-up from the study:

- Participant not able to attend follow-up visits, but may still be contacted by telephone or email for 12 months time point enquiry into adverse events/MACE
- By assessment of the investigator or clinician not to continue due to safety concern (e.g. adverse event, pregnancy)
- Palliation for end of life care

